3.1.3 Reported nausea in at least 28% of participants

[figure not shown]
If 7 or more participants report nausea with combination hydroxyzine and varenicline, this investigational treatment will be viewed unpromising and no additional participants will be enrolled.

3.1.4 Stepwise Evaluation Algorithm

3.2 STUDY PLAN

After obtaining informed consent, adult smokers will be enrolled into the study. There will be an observational period of at least five days to obtain baseline data on use of combustible cigarettes and stress/anxiety and nausea symptoms.

Varenicline Dose = 0.5 mg QPM x 3 days, then 0.5 mg BID x 4 days, then 1.0 mg BID x 11 weeks Hydroxyzine Dose = 50 mg QPM x 3 days, then 25 mg QAM + 50 mg QPM

3.3 Point of Enrollment

Participants will be enrolled after screening once all safety laboratory results have been received and reviewed by the medical staff (MD or PA). Study drugs will be dispensed starting at V2, and at each subsequent visit until the End-Of-Study.

3.4 STUDY AND SESSION DURATIONS

The expected duration of the study, from first participant, first visit, through last participant, last visit will be approximately one year. The total duration for a participant will be approximately 14-16 weeks.

- The Screening Session (Visit 1) will last approximately three hours.
- The other study sessions will last approximately one hour.

4 PARTICIPANT INVOLVEMENT

4.1 SELECTION OF STUDY POPULATION

Healthy, cigarette smoking adults, age 19-65 years, with no restriction on gender, race and ethnicities, or social-economic status, who have smoked an average of at least 10 commercially available cigarettes per day for the last 12 months will be screened for enrollment in this study.

The study will screen and enroll at both Rose Research Center locations, located in Raleigh and Charlotte, North Carolina.

4.1.1 Inclusion Criteria

Each participant must meet all the following inclusion criteria before enrollment:

Inclusion Criteria

- 1. Has signed the ICF and is able to read and understand the information provided in the ICF.
- 2. Is 19 to 65 years of age (inclusive) at screening.
- 3. Smokes at least 10 commercially available cigarettes per day for the last 12 months.
- 4. Has an expired air CO reading of at least 10 ppm at screening.
- 5. Express a desire to quit smoking within the next 30 days at screening.
- 6. Willing and able to comply with the requirements of the study.
- 7. Participant owns a smart phone with text message and data capabilities.

4.1.2 Exclusion Criteria

Potential participants who show or report indications of or self-report a diagnosis of conditions listed below may be excluded from the study. If the study physician (or designee) determines through the course of pre-screening, or a physical screen, medical history, physical findings, current medications, ECG, or laboratory findings suggests one of the conditions listed below, or findings reveal other information that may potentially jeopardize the participants' safe participation, then they may be excluded. For medical conditions that do not appear below, the participant may be enrolled if the study physician (or designee) does not feel that the medical condition would jeopardize safe study participation or data validity.

Exclusion Criteria

- 1. Is unhealthy or cannot participate in the study for any reason (e.g., medical, psychiatric, and/or social reason) as judged by the Investigator or designated medical staff based on all available assessments from the screening period (e.g., safety laboratory, vital signs, physical examination, ECG, concomitant medications and medical history).
- 2. PHQ-9 score greater than 9, or a score greater than 0 on item #9 ("Thoughts that you would be better off dead, or of hurting yourself in some way") at screening.
- 3. High blood pressure (systolic > 150 mmHg or diastolic >95 mmHg) at screening.

Exclusion Criteria

- 4. Body mass index (BMI) less than 15.0 kg/m² or greater than 40.0 kg/m².
- 5. Coronary heart disease, structural cardiac disease, cardiac dysrhythmias, abnormal ECG (e.g. prolonged QT_c), syncope, cardiac chest pain, or history of heart attack or heart failure.
- 6. Has received psychotherapy or behavioral treatments potentially impacting symptoms of depression, anxiety, or nicotine withdrawal within 30 days of screening, or during the study.
- 7. Taking antidepressants, psychoactive medications (e.g. antipsychotics, benzodiazepines, hypnotics) or medications that prolong QT_c .
- 8. Positive urine drug test for cocaine, THC, opiates, amphetamines or methamphetamines.
- 9. Use of smokeless tobacco (chewing tobacco, snuff), cigars, pipes, hookah, e-cigarettes, nicotine replacement therapy or other smoking cessation treatments within 14 days of enrollment.
- 10. Pregnant or nursing (by self-report) or has a positive pregnancy test.

4.1.3 Women of Childbearing Potential

Pregnant or breastfeeding women will be excluded from the study. All females will undergo a serum pregnancy test at screening (Visit 1) and a urine pregnancy test at each subsequent visit. Heterosexually active females of childbearing potential (not post-menopausal) must agree to use medically acceptable contraceptives during the study. Medically acceptable contraceptives include: (1) surgical sterilization (such as a tubal ligation, hysterectomy, or Essure), (2) approved hormonal contraceptives (such as birth control pills, patches, implants or injections), (3) barrier methods (such as a condom or diaphragm) used with a spermicide, or (4) an intrauterine device (IUD). Contraceptive measures such as Plan BTM, sold for emergency use after unprotected sex, are not acceptable methods for routine use. Female participants will be encouraged in the consent form to notify study staff if they believe a change in their pregnancy status has occurred during the trial.

Post-menopause is defined as the time after which a woman has experienced 12 consecutive months of amenorrhea (lack of menstruation).

4.2 RECRUITMENT STRATEGIES

Participants will be selected through IRB approved generic recruitment advertisements which are specifically designed to recruit participants into the volunteer database for future smoking and tobacco use related research at the Rose Research Center. For this database, many of the participants have provided basic smoking history data along with demographic information, which will allow selection of potentially interested participants.

Participants who call in will be screened into the volunteer database, and if they pre-qualify, will be offered the option to prescreen for this protocol.

Participants will be contacted only with IRB approved appropriate materials and information submitted along with this protocol. These documents will include a brief description of the study and information on how to prescreen for participation. Participants will be contacted by phone, email and text message prompting interested participants to prescreen through an electronic screen form.

4.2.1 Pre-Screening

Pre-screening will be completed prior to V1 for all participants. Participants will be provided with a set of IRB approved questions directly related to the inclusion and exclusion criteria. Based upon the outcome of these questions, potential participants may be scheduled for a screening visit (V1).

4.3 Participant Retention in the Study

All candidates who schedule a screening visit (V1) will receive a series of email, text, and telephone reminders; participants are also permitted through these communications to confirm, cancel, or reschedule all their appointments.

4.4 DISCONTINUATION OF PARTICIPANTS FROM STUDY

Discontinued participants will include both participants who withdraw from the study (participant's decision) or participants who are discontinued from the study (following Investigator's decision). A participant can only be discontinued from the study after enrollment. Participants that are not enrolled are considered screen failures.

Participants will be informed that they are free to withdraw from the study at any time. Participants should be questioned for the reason of premature withdrawal from the study, although they are not obliged to disclose it.

Participants discontinued from the study cannot re-enter the study.

4.4.1 Participants must be discontinued from the study for any of the following reasons:

- No-show to appointments and unable to reschedule within the visit window.
- Withdrawal of informed consent.
- Any adverse effect or condition that would jeopardize continued safe study participation.
- Pregnancy test is positive.
- Discontinuation is considered to be in the best interest for the participant or for other participants participating to the study, as judged by the Investigator or designee.

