2.1.4 Side Effects and Tolerability data

Tolerability will be evaluated using open-ended as well as targeted side effect assessments at each visit. Participants will be queried on their level of nausea via daily SMS text messages.

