4.5 Lost to Follow-up

A reasonable number of attempts to contact the participant (including written correspondence and phone calls) should be made and documented in the source documents. The date of the last contact (e.g. last visit, last phone call) should also be recorded in the source document. When the PI(s) or designee(s) declare(s) a participant is lost to follow-up, the lost to follow-up date will be recorded and will correspond to the date of the end of study (EOS) of the participant.

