4.8.2 All other visit Windows

Participants may attend sessions up to four-calendar day's pre or post the scheduled visit.

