8.3 Pre-Quit Session (V2)

After completion of a minimum five-day observational period, participants will come to the Center for assessment, training (including brief quit smoking counseling), and dispensing of study drugs. The quit date will be scheduled for the day after Visit 3, and seven days after commencing the study drugs. The sequence of the following assessments will be at the discretion of the Investigator or designee.

- Document concomitant disease and medication changes
- Physical examination (if indicated)
- Expired air CO breath test
- Vital signs (blood pressure, heart rate, respiratory rate)
- Weight
- Brief smoking cessation counseling (QuitAssist Counseling Handout)
- Urine pregnancy test (all females)
- Dispensing of study drugs
- Verification of proper use of the SMS messaging (refresher training, if needed)
- Questionnaires
 - Employment History
 - o FTND
 - PSS-10
 - o 6-Item STAI
 - Adverse Effects Questionnaire
 - Patient Health Questionnaire (PHQ-9)
 - Wisconsin-Predicting Patient's Relapse (WI-PREPARE)
 - Modified Cigarette Evaluation Questionnaire (mCEQ)
 - Smoking Status (daily via SMS survey, commence after visit)
 - o Medication Compliance (daily via SMS survey, commence after visit)

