8.5 Post-Quit Sessions (V4-V7)

Sessions scheduled after the quit-smoking date will be conducted at 2 weeks after the quit date and then at 4-week intervals until the end of the 12-week treatment period. The sequence of the following assessments will be at the discretion of the Investigator or designee.

- Document concomitant disease and medication changes
- Physical examination (if indicated)
- Expired air CO breath test
- Vital signs (blood pressure, heart rate, respiratory rate)
- Weight
- Brief review of smoking cessation counseling (if indicated)
- Urine pregnancy test (all females)
- Collection and dispensing of study drugs (collection only at the EOS visit)
- Assess medication compliance
- Verification of proper use of the SMS messaging (refresher training, if needed)
- Questionnaires
 - o FTND
 - o PSS-10
 - MNWS
 - o 6-Item STAI
 - o Adverse Effects Questionnaire
 - Patient Health Questionnaire (PHQ-9)
 - Smoking Status (review with participant and continue daily via SMS survey until End of Study)
 - Medication Compliance (review with participant and continue daily via SMS survey until End of Study)

8.6 6-Month Follow Up

Participants who successfully complete the study and are abstinent at the final visit (V7), will be contacted six months after the quit day utilizing an automated SMS messaging system, to ascertain their current smoking status.

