14.4 Participant Information and Consent

It is the responsibility of the investigator to provide each participant with full and adequate verbal and written information using the IRB-approved informed consent form (ICF), including the objective and procedures of the study and the possible risks involved before inclusion in the study. Informed consent must be obtained prior to performing any study-related procedures.

The signed and personally dated original and completed ICF(s) must be kept by the Investigator and filed in the Investigator study file at the site or with the participant's files and a copy must be given to the participant. The participant will be informed that if they discontinue from the study, the data collected until the point of discontinuation will be maintained as part of the study data and the samples collected prior to discontinuation will be analyzed, unless they refuse in writing.

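### Section 4.4.1 turns a missed visit window into permanent study exit, so later SMS and CO data from a participant who can still be reached are lost by rule

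*Combined protocol and SAP*

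**What the plan says.** Section 4.4.1 gives reasons for which discontinuation from the study is compulsory. The first is "No-show to appointments and unable to reschedule within the visit window". Of the listed reasons, only the last, on best interest, is expressly left to the investigator's judgement. Section 4.4 adds: "Participants discontinued from the study cannot re-enter the study".

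The window for every visit except V2 is in 4.8.2: "Participants may attend sessions up to four-calendar day's pre or post the scheduled visit". V2 has its own 30-day limit (4.8.1) and comes before any study drug.

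People who cannot be reached have a separate rule in 4.5, which begins with "A reasonable number of attempts to contact the participant".

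The nausea data do not depend on attendance. Section 2.1.4 says: "Participants will be queried on their level of nausea via daily SMS text messages". CO is measured at laboratory sessions (7.2.5). On what survives an exit, 14.4 tells participants that "the data collected until the point of discontinuation will be maintained as part of the study data". No section provides for SMS or CO collection after a missed window.

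**The concern.** The item merges two decisions: whether it is safe to keep supplying drug, and whether to keep observing the participant. Since 4.5 already deals with people who cannot be found, what 4.4.1 adds is the removal of people who can. Such a person could still answer a daily text and could still attend the next visit for a CO reading.

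The protocol takes the opposite approach elsewhere. Section 9.4 asks participants whose treatment is stopped over side effects to stay on for outcome assessment. Someone who can attend only five days late has no such route.

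Nausea is the pilot's main hypothesis and the only go/no-go variable (13.1.1, 13.1.2). Exit at V3 to V6 also prevents full observation of the primary abstinence period, weeks 8 to 11 after quitting. Section 13.1.1 scores as non-abstinent those lost to follow-up or relapsed; a reachable participant removed by rule is not clearly either. For nausea, 12.4 imputes nothing while 13.1.2 uses fixed counts of 25 and 50, so the plan does not say how a removed participant is counted.

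**Working it through.** **1. Follow-up lost at each visit.** Take day 0 as the first dose and treatment as 12 × 7 = 84 days. Section 8.3 says: "The quit date will be scheduled for the day after Visit 3, and seven days after commencing the study drugs". That puts V3 on day 6 and the quit date on day 7. Section 8.5 places later visits at "2 weeks after the quit date and then at 4-week intervals until the end of the 12-week treatment period". So V4 = 7 + 14 = 21, V5 = 21 + 28 = 49 and V6 = 49 + 28 = 77. V7 is taken at the end of treatment, about day 84. Each window closes at the visit day + 4.

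| Missed visit | Day | Window closes | SMS days lost of 84 |
|---|---|---|---|
| V3 | 6 | 10 | 74 (88%) |
| V4 | 21 | 25 | 59 (70%) |
| V5 | 49 | 53 | 31 (37%) |
| V6 | 77 | 81 | 3 (4%) |
| V7 | 84 | after treatment | 0 |

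Mean with exits spread evenly: (74 + 59 + 31 + 3 + 0) / 5 = 33.4 days, and 33.4 / 84 = 40%.

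**2. How many would be removed.** The documents give no missed-window rate. With an assumed rate m per visit over five visits, cumulative removal is 1 − (1 − m)^5: 4.9% at m = 1%, 9.6% at 2% and 18.5% at 4%.

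**3. The plan's nausea rule, reproduced.** With X1 and X2 each Binomial(25, p) and the 13.1.2 limits:

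P(go) = P(X1 ≤ 3) + Σ over k = 4 to 6 of P(X1 = k) × P(X2 ≤ 10 − k).

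- p = 0.30: 0.0332 + 0.0572 × 0.3407 + 0.1030 × 0.1935 + 0.1472 × 0.0905 = 0.086 (13.1.3 states 9%).
- p = 0.15: 0.861 (stated 86%).
- p = 0.10: 0.985 (stated 98%).

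**4. Effect of exits on the false-go rate at a true 30%.**

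- If exits are left out, following the observed-values rule in 12.4, and exit is unrelated to nausea, p stays at 0.30. With the counts of 25 and 50 still filled, the rate stays at 8.6%.
- If exits stay in the denominator as free of nausea, let r be the share removed and f the share of their nausea that first arises after exit. Observed p = 0.30 × (1 − r × f).

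| r | f | Observed p | False-go |
|---|---|---|---|
| 5% | 10% | 0.2985 | 8.9% |
| 10% | 10% | 0.2970 | 9.3% |
| 10% | 40% | 0.2880 | 11.6% |
| 10% | 50% | 0.2850 | 12.5% |

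The value f = 40% follows from the 40% mean in step 1 if nausea onset is uniform over treatment. A larger f needs exits weighted to early visits or later-skewed onset. A smaller f applies if most nausea appears early. Both r and f are assumptions.

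**5. Abstinence.** Assume a one-sided 5% test with N = 50. The exact rule for finding abstinence below 45% is 16 or fewer of 50, with probability 4.3% at a true 45%. If a share r is removed and a share q of them were abstinent but scored as not, observed p = 0.45 − r × q. For r = 5%, q = 10%, p = 0.445 and the error is 5.0%. For r = 10%, q = 45%, p = 0.405 and it is 14.0%. This applies only if the 45% benchmark scored drop-outs differently, which the documents do not show.

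**The case against.** The trigger has two parts: a no-show, and failure to rebook within a window that spans nine days. Participants get email, text and telephone reminders for the screening visit and may reschedule all appointments (4.3), and they are paid for each visit (4.7). Many who still miss the window may in fact be unreachable, so in practice the item may overlap with 4.5. Nor does any sentence expressly stop the SMS; that follows from study discontinuation read with 14.4. Both points stand as limits on size. They do not alter the rule, which is compulsory and does not ask whether the person can be contacted.

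Visits also carry the pregnancy test, PHQ-9, blood pressure and adverse-effects form, so a missed one is a genuine safety gap. That is a reason to hold drug, but not to stop asking about nausea.

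Drug is dispensed only at visits, so part of the later SMS series would come after the supply has run out and would not describe nausea on the combination. This also stands: the days in the table are days of follow-up, not all of them on-treatment data.

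A reader might infer that the rule costs most of the SMS record wherever it strikes. That holds for V3 and V4 but not for V6 or V7. A reader might also infer that abstinence is biased down against the 45% benchmark. The documents do not say how that benchmark treated drop-outs, and no go/no-go branch uses abstinence.

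**Conclusion.** The concern holds as a design point: the text requires permanent exit after a missed window at V3 to V7, and no other section softens it for this case. No stated figure in the plan is wrong.

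The loss of follow-up is large for an early miss (88% of SMS days at V3) and negligible for a late one. The effect on the decision runs from nil to modest: 8.6% if exits are omitted and unrelated to nausea, and about 11.6% under 10% removal, scoring as free of nausea, evenly spread exits and uniform onset. The 12.5% figure needs 50% of nausea to arise after exit, which the documents give no reason to expect. The abstinence range of 5.0% to 14.0% is conditional in the same way and should not be read as an expected bias.

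The sponsor should make the change because it is cheap and, with at most 50 participants, each avoidable loss counts. Confidence is medium, since neither the missed-window rate nor the timing of nausea is given.

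**What to change.** For V3 to V7, delete the missed-window item from the mandatory reasons for study exit. Make it a reason to hold study drug until the missed safety checks (pregnancy test, PHQ-9, blood pressure, adverse-effects form) are done, with medical staff deciding on any restart.

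Unless consent is withdrawn, continue the daily SMS and all remaining scheduled visits, including the V7 CO reading. Flag off-window and off-drug data. State that anyone without outcome data is scored as non-abstinent under 13.1.1.

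Leave the V2, pregnancy, safety and best-interest rules as they are. A fixed extension of the visit window or an automatic shift of the quit date is not needed. Either could open a dosing gap near the step up to 1 mg twice daily, for which the protocol has no restart rule.

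The cost is protocol wording, some flagged off-window or off-drug data, possible dosing gaps while checks are outstanding, deviation records (reported to the IRB within 10 days where 12.2 requires), and a few extra SMS and visit payments.

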4.5 Lost to Follow-up

A reasonable number of attempts to contact the participant (including written correspondence and phone calls) should be made and documented in the source documents. The date of the last contact (e.g. last visit, last phone call) should also be recorded in the source document. When the PI(s) or designee(s) declare(s) a participant is lost to follow-up, the lost to follow-up date will be recorded and will correspond to the date of the end of study (EOS) of the participant.

4.6 VIOLATION OF INCLUSION/EXCLUSION CRITERIA

Participants who, after signing the ICF, do not meet the inclusion and exclusion criteria will not be enrolled in the study and will be considered screen failures. Re-screening for the study is not permitted.

4.7 Participant Compensation

There will be a payment of \$25 for the screening session, \$50 for Visit 2 through Visit 6, and \$100 for Visit 7. Participants will also receive payments of \$5/day for responding to daily text messages.

If participants are asked by study staff to return to the Center to complete or redo parts of the sessions in situations of equipment malfunctions or other circumstances that are beyond the participants' control, participants may be reimbursed for mileage (based on the IRS's mileage rate).

Participants who decide to withdraw from the study will be paid for the part of the study they have completed.

4.8 Session and Response Windows

4.8.1 V2 Session Window

Participants may attend V2 up to 30 days post Screening Session (V1).

4.8.2 All other visit Windows

Participants may attend sessions up to four-calendar day's pre or post the scheduled visit.

4.8.3 SMS Response Window

The SMS response window will be open until the next SMS message is sent.

5 HYDROXYZINE

5.1 DESCRIPTION OF HYDROXYZINE

Hydroxyzine is an FDA approved first-generation antihistamine of the diphenylmethane and piperazine class that has antiemetic, anxiolytic, and sedative effects. Hydroxyzine's effects are primarily derived due to its actions as a potent H1 receptor inverse agonist. It also acts as an antagonist on the 5-HT2A, D2, and α 1-adrenergic receptors. Because of its antiserotonergic effects, as well as the antagonistic effects on multiple receptor systems in the brain, hydroxyzine is noted to have strong anxiolytic properties, as well as mild antiobsessive and antipsychotic properties. Even with its effective sedative, hypnotic, and anxiolytic effects, hydroxyzine does not demonstrate any of the abuse, dependence, addiction or toxicity potential associated with medications within the same therapeutic range (such as benzodiazepines or nonbenzodiazepine hypnotics). 13

LLorca et al. demonstrated the safety and efficacy of hydroxyzine in the treatment of generalized anxiety disorder.²⁰ A common adverse event for hydroxyzine (occurring 10% or more) is drowsiness. All other adverse events occurred less than 10% or were of unknown incidence. This includes dry mouth, cough, unusual tiredness, and irregular or slow heart rate.²¹

A Cochrane Review from 2014 which looked at interventions for nausea and vomiting in early pregnancy noted that hydroxyzine had a statistically significant improvement in nausea at a dose of 25 mg twice a day, when compared with placebo (see figure 2).²⁴ It also noted that only 7% of the participants using hydroxyzine reported only "slight drowsiness" while taking this medication at this particular dose.²⁴ No other adverse effects were reported in this review.

[figure not shown]

Figure 2: From Matthews A, Haas DM, O'Mathúna DP, Dowswell T. Interventions for nausea and vomiting in early pregnancy. Cochrane Database Syst Rev. 2015;(9):CD007575. doi:10.1002/14651858.CD007575.pub4

A study published in 2012 evaluated the efficacy of combining hydroxyzine with ondansetron for treatment of side effects associated with chemotherapy regiments which utilized highly emetogenic drugs. This study demonstrated that complete control of acute emesis was achieved in 56% of pediatric cancer patients utilizing both antiemetic medications versus only 22% utilizing ondansetron without hydroxyzine (p=0.006). This study also reported that patients and parents noted "...significantly better sleeping quality, appetite, activity and mood..." for those patients taking ondansetron with hydroxyzine versus without hydroxyzine. The dose of hydroxyzine used was 1 mg/kg/dose, equivalent to 77 mg for an average adult female and 89 mg for an average adult male (an average American female weighs 170 lbs. and an average American male weighs 197 lbs. according to the CDC). Dosing for this study will be based on minimizing the risk of sedation (25 mg AM dosing) while optimizing the beneficial effects of the study drug (50 mg PM dosing). Participants will be titrated to these doses in a similar fashion as the titration of varenicline, allowing for dose adjustment based on daily evaluation of potential side effects.

